2.1. Study Objectives, Endpoints, and Estimands

Objectives	Endpoints
Primary:	Primary:
• To evaluate the safety, and local and systemic tolerability, of PF-07295324 and PF-07259955, following multiple doses of topically administered PF-07295324 or PF-07259955, on approximately 20% BSA in healthy adult participants.	 Incidence and severity of systemic AEs, safety laboratory tests, vital signs (including blood pressure and pulse rate), and heart rhythms as assessed via 12-lead electrocardiogram (ECG). Incidence and severity of application site AEs as assessed by Draize score.
Secondary:	Secondary:
• To characterize plasma PK following multiple topical applications of PF-07295324 and PF-07259955.	 Plasma PK of multiple topical doses of PF-07295324 and PF-07259955, as data permits: Day 1: C_{max}, T_{max}, C_{avg}, C_{trough}, AUC_{tau} Day 10: C_{max}, T_{max}, C_{avg}, C_{trough}, AUC_{tau}, R_{ac} (C_{max}), R_{ac}(AUC_{tau}), t₂, CL/F, and V₂/F
CCI	

2.2. Study Design

C4711001 is an investigator- and participant-blinded, interventional, randomized, vehicle-controlled, Phase 1 study to evaluate the safety, and local and systemic tolerability and pharmacokinetics of maximum feasible formulation of topical JAK inhibitors, PF-07295324 (0.12%) and PF-07259955 (2%) in healthy adult participants.

This study will enroll healthy adult participants in ≤ 4 cohorts: 2 planned cohorts and 2 optional cohorts. Approximately 6 participants will be enrolled in each cohort, randomized as 4 active: 2 vehicle. Cohort 1 and the optional Cohort 3 will be assigned to PF-07295324/vehicle, administered topically as an ointment. Cohort 2 and the optional Cohort 4 will be assigned to PF-07259955/vehicle administered topically as a cream.

Participants will be enrolled in the optional cohorts in a sequential design to the respective planned cohort, as shown in Figure 1. Planned cohorts assigned to different interventions may progress simultaneously. Similarly, optional cohorts assigned to different interventions may progress simultaneously (Figure 1).

Up to 2 optional cohorts (Cohort 3 and Cohort 4) of up to 6 participants/cohort may be enrolled in this study. Participants enrolled in the optional cohort will be randomized to either active or vehicle (4:2). The optional cohorts may be used to explore lower strength formulations on approximately 20% BSA, or to repeat the maximum feasible formulation on lower body surface area, or to administer maximum feasible formulation at a less frequent dosing regimen on approximately 20% BSA. Participants enrolled in the optional cohorts will be guided by the same stopping criteria as the planned cohorts.

[figure not shown]

Figure 1. Study Schema

- a. PF-07295324 (0.12%)/vehicle in Cohort 1 or PF-07259955 (2%)/vehicle in Cohort 2, will be topically applied on approximately 20% body surface area, Q12H from D1 to D9; only morning (AM) dose will be applied on D10.
- b. Based on review of emerging safety from Cohort 1, optional Cohort 3 may be enrolled to explore lower formulation strength of PF-07295324, topically applied on approximately 20% BSA or PF-07295324 (0.12%) on lower body surface area or at a less frequent dosing regimen on approximately 20% BSA.
- c. Based on review of emerging safety assessments from Cohort 2, optional Cohort 4 may be enrolled to explore lower formulation strength of PF-07259955 topically applied on approximately 20% BSA or PF-07259955 (2%) on lower body surface area or at a less frequent dosing regimen on approximately 20% BSA.

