1.2. Schema

Figure 1. Study Schema

a. PF-07295324 (0.12%)/vehicle in Cohort 1 or PF-07259955 (2%)/vehicle in Cohort 2, will be topically applied on approximately 20% body surface area or less than or equal to 4000 cm², Q12H from D1 to D9; only morning (AM) dose will be applied on D10.

b. Based on review of emerging safety from Cohort 1, optional Cohort 3 may be enrolled to repeat the PF-07295324 dose studied in Cohort 1, explore lower formulation strength of PF-07295324, topically applied on approximately 20% BSA or PF-07295324 (0.12%) on lower body surface area or at a less frequent dosing regimen on approximately 20% BSA or less than or equal to 4000 cm².

c. Based on review of emerging safety assessments from Cohort 1, Cohort 2 and Cohort 3, optional Cohort 4 may be enrolled to study either PF-07295324 or PF-07259955 by repeating doses studied in previous cohort(s), exploring lower formulation strength topically applied on approximately 20% BSA or investigating the safety of maximum feasible formulation on lower body surface area or at a less frequent dosing regimen on approximately 20% BSA or less than or equal to 4000 cm².

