j. In Cohorts 1 and 2, study intervention/vehicle will be applied, on D1 to D9, Q12H. PM dose will be applied approximately 12±1 hours post-AM dose. On D10, study intervention/vehicle will be applied, at AM only. No PM dose will be applied on D10. PF-07295324/vehicle ointment will be applied to participants enrolled in Cohort 1 and in optional Cohort 3. PF-07259955/vehicle cream, will be applied to participants enrolled in Cohort 2. PF-07295324 or PF-07259955 may be studied in optional Cohort 4.

- k. Application sites will be identified at screening. Examination of application sites will be conducted at screening and on D-1. On D1 to D10, skin irritation assessment using Draize's scoring (Table 5) will be performed prior to each application of the investigational product. On D11 (approximately 24H post last dose) and on D12 prior to discharge, skin irritation assessment using Draize's scoring will be performed. Refer to Section 8.2.5.
- 1. At screening, FSH test will be performed in females only, to confirm postmenopausal status.
- m. Safety labs will be collected at screening, admission (D-1), during in-patient dosing as specified in Table 1, at discharge, and at early termination.
- n. See Table 2 for detailed blood sampling schedule for PK on D1 and D10. Samples will be collected at pre-AM application on D2, D5 and D7. PK sample will be collected on D12, prior to discharge.

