Participants confirming eligibility according to Section 5 will be admitted to the CRU on Day -1. On Day 1, application sites of all participants will be assessed, prior to the administration of study intervention/vehicle. Dermal reactions at the application site will be assessed clinically using a visual grade that rates the degree of erythema, edema, and other signs of skin irritation. Participants enrolled in Cohort 1 and Cohort 2, with no dermal site reactions at pre-dose on Day 1, will receive multiple topical doses of study intervention or vehicle, Q12H from Day 1 to Day 9, and only AM application on Day 10. All AM doses will be administered approximately 60 minutes following shower, if participants choose to shower; all PM doses will be administered approximately 12±1 hour post-AM dose. Participants will be discharged on Day 12 following the completion of all scheduled procedures as per SoA. Participants will be scheduled for a follow-up phone contact on Study Day 41±3 days.

Up to 2 optional cohorts (Cohort 3 and Cohort 4) of up to 6 participants/cohort may be enrolled in this study. Participants enrolled in the optional cohort will be randomized to either active or vehicle (4:2). The optional cohorts may be used to repeat the doses studied in previous cohorts, explore lower strength formulations on approximately 20% BSA, or to repeat the maximum feasible formulation on lower body surface area, or to administer maximum feasible formulation at a less frequent dosing regimen on approximately 20%

BSA. Participants enrolled in the optional cohorts will be guided by the same stopping criteria as the planned cohorts.

If a participant has any clinically significant, study related abnormalities at the conclusion of a scheduled inpatient portion of the study, the Pfizer medical monitor (or designated representative) should be notified and the participant may be asked to remain in the CRU until such abnormalities are deemed not clinically significant, or it is safe for outpatient follow-up. Participants who experience a treatment-related AE will continue to be followed to resolution or stabilization of the event as agreed upon by the investigator and sponsor. Participants who discontinue for non-safety related reasons prior to end of the study may be replaced, at the discretion of the principal investigator (PI) and the sponsor.

The planned duration of participation from screening to follow-up is approximately 10 weeks.

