6.5. Dose Modification

No dose modification is anticipated for Cohort 1 and Cohort 2 in this study. Dose and dosing regimen in Cohort 3 and Cohort 4 may be determined based on review of emerging data from Cohort 1 (for Cohort 3 only) and Cohort 1, Cohort 2 and Cohort 3 (for Cohort 4 only).

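### Does the SAP's older description of optional Cohort 4 leave the PK summary of a repeated regimen unsettled?

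*SAP*

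**What the plan says.** **SAP.** The version history ties version 1 (03 Feb 2022) to the original protocol of 06 Dec 2021. Section 2.2 says "Cohort 2 and the optional Cohort 4 will be assigned to PF-07259955/vehicle administered topically as a cream". Note c to its schema says, on the basis of Cohort 2 data, that "optional Cohort 4 may be enrolled to explore lower formulation strength of PF-07259955 topically applied on approximately 20% BSA", with a smaller area or less frequent dosing as alternatives. The general sentence is similar: "The optional cohorts may be used to explore lower strength formulations on approximately 20% BSA", or the maximum formulation on a smaller area or less often. Each of these uses changes the regimen.

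**Current protocol.** Note j to the Schedule of Activities (Section 1.3.1) says "PF-07295324 or PF-07259955 may be studied in optional Cohort 4". Section 4.1 says "The optional cohorts may be used to repeat the doses studied in previous cohorts", and note b to the schema in Section 1.2 says "optional Cohort 3 may be enrolled to repeat the PF-07295324 dose studied in Cohort 1".

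**PK outputs.** SAP Section 6.2.1 asks for PK parameters by cohort and dose, and later by treatment group and day. Concentration summaries and the mean and median plots are also described once by treatment group and once by cohort and dose. Protocol Section 9.3.3.2 uses treatment group. Neither document defines the term.

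**The concern.** A SAP that describes a design narrower than the one that may be run can leave a case without an analysis rule. Here the case is an optional cohort given exactly the regimen of Cohort 1 or Cohort 2. Read by cohort, one regimen would appear as two separate sets of about four active participants. Read by a treatment group defined by regimen, it would appear as one set of about eight.

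SAP Section 7 allows the sponsor unblinded reviews during the study, and Section 7.2 includes PK data in what may be reviewed. The layout to emphasise could therefore be picked after concentrations are known. PK is the secondary objective and is meant to support development of both compounds, so it is reasonable to ask whether the summary for a regimen is fixed in advance.

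**Working it through.** **1. The plan's own figure.** Protocol Section 9.5 gives approximately 12 participants in the planned cohorts: 2 cohorts × 6 = 12. It reproduces. At 4 active to 2 vehicle, each cohort has 6 × 4/6 = 4 active participants.

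**2. When the two groupings differ.**

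| Use of optional cohort | By cohort and dose | By regimen |
|---|---|---|
| None enrolled | 4 | 4 |
| Lower strength, smaller area or less frequent dosing | 4 and 4 | 4 and 4 |
| One exact repeat | 4 and 4 | 4 + 4 = 8 |
| Cohorts 3 and 4 both repeat Cohort 1 | 4, 4 and 4 | 4 + 4 + 4 = 12 |

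For PF-07259955 the most is about 4 + 4 = 8 (Cohorts 2 and 4), because Cohort 3 is reserved for PF-07295324. All counts are approximate, since cohort size is approximate and some withdrawals may be replaced. Only the last two rows differ.

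**3. Does any analysis instruction depend on the Cohort 4 text?** Cohort 4 is named only in SAP Section 2.2. The PK analysis sets in Section 4 admit anyone who received either compound. Section 6.1.1 groups vehicle by ointment or cream, not by cohort, so it works whichever compound Cohort 4 receives. Sections 6.1.1.1 to 6.1.1.4 summarise safety by treatment, and Section 4.1 assigns participants as treated. None of these changes if Cohort 4 takes PF-07295324 or repeats a dose.

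**4. What Section 6.2.1 yields for an exact repeat.** Its list of concentration presentations is explicit: summaries and mean, median and individual plots by cohort and dose, plus a listing of every concentration by participant, cohort and dose. PK parameters are listed as well. The treatment-group sentences largely carry over Protocol Section 9.3.3.2. An analyst can produce both layouts from the same data, and neither contradicts the other.

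**5. How much could the layout matter numerically?** The documents give no between-subject CV and plan no confidence intervals, so this is illustration only. Assume log-normal data, with s = √ln(1 + CV²).

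The 95% interval factor around a geometric mean is exp(t(0.975, n−1) × s/√n), where t/√n = 1.591, 0.836 and 0.635 for n = 4, 8 and 12. At an assumed CV of 50%, s = √ln 1.25 = 0.472, so the factor at n = 4 is exp(1.591 × 0.472) = 2.12.

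The chance that two sets of 4 on one regimen differ at least 1.5-fold in geometric mean is 2 × [1 − Φ(ln 1.5/(s√(2/4)))]. At CV 50% this is 2 × [1 − Φ(0.405/0.334)] ≈ 0.22.

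| Assumed CV | n = 4 | n = 8 | n = 12 | Chance of ≥1.5-fold gap |
|---|---|---|---|---|
| 30% | 1.60 | 1.28 | 1.21 | 0.05 |
| 50% | 2.12 | 1.48 | 1.35 | 0.22 |
| 100% | 3.76 | 2.01 | 1.70 | 0.49 |

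These figures show that four participants estimate a mean poorly. They do not show an error in the plan, because it calculates no such interval and makes no comparison between cohorts.

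**6. The rule requiring at least 3 evaluable values.** SAP Section 5.3 words this rule per dose, not per cohort. If it were nevertheless applied within a cohort, and each participant's parameter were evaluable with assumed probability 0.5, 0.7 or 0.9, the binomial chance of reaching 3 would be 0.31, 0.65 or 0.95 with 4 participants. With 8 it would be 0.86, 0.99 or 1.00. The SAP's wording does not call for the within-cohort reading, and individual parameters are listed in any case.

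**The case for a change.** The best case for a change is that the fix is cheap and the SAP text is out of date. SAP Section 2.2 declares no departure from the protocol; it simply describes the earlier design. A term used for three kinds of output ought to be defined, and naming one main display before unblinded review would remove any choice made after the data are seen.

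The description is indeed outdated and the term undefined. A tidy SAP would correct both, and could say whether same-regimen cohorts are shown together, apart or both ways. The protocol is not uniform either. Its synopsis (Section 1.1) and Section 4.3.2 refer to Cohorts 1 and 2 as the basis for the optional cohorts, while schema note c and Section 6.5 give Cohorts 1 to 3 for Cohort 4. The synopsis also speaks of one optional cohort per intervention just before opening Cohort 4 to either compound. Those passages need reconciling as text.

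The step from there to a fault in the analysis does not stand. A choice made after seeing data does harm when it can alter a test, an estimate carried into a decision rule, or what a reader is able to see. Here nothing is tested, no PK criterion is set, and all individual values are listed. Whether pooled or by-cohort output leads is a presentation preference on which statisticians differ: pooling uses all the data on a regimen, while separate display shows whether sequential cohorts agree.

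**Conclusion.** No change to the analysis plan follows. The Cohort 4 text reflects a SAP tied to the original protocol, and the undefined treatment group is a detail that analysts can fill sensibly by showing a repeated regimen both ways. The effect is nil unless an optional cohort exactly repeats a regimen. In that case it is limited to whether the secondary descriptive PK shows sets of about 4 or one set of about 8 (12 at most, for PF-07295324 only). No bias and no gain in precision is claimed, because the intervals in the check rest on assumed CVs and are not planned outputs. Primary safety summaries, as-treated assignment and vehicle grouping are unchanged.

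The conclusion assumes that PK stays descriptive with full listings, as SAP Sections 5.1 and 6.2.1 state. The sponsor's data standards, to which both documents refer for summary conventions, are not available here and may already settle the grouping.

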3. ENDPOINTS AND BASELINE VARIABLES: DEFINITIONS AND CONVENTIONS

3.1. Primary Endpoint(s): Safety Endpoints

- Incidence and severity of systemic AEs, safety laboratory tests, vital signs (including blood pressure and pulse rate), and heart rhythms as assessed via 12-lead electrocardiogram (ECG).
- Incidence and severity of application site AEs as assessed by Draize score.

The following data are considered in standard safety summaries (see protocol for collection days, baseline assessment, and list of parameters):

- AEs;
- Safety laboratory tests;
- Vital signs (Blood Pressure and Pulse rate);
- ECG.

3.1.1. Adverse Events

An adverse event (AE) is considered a Treatment-Emergent Adverse Event (TEAE) if the event started during the effective duration of treatment. All events that start on or after the first dosing day and time/start time, if collected, but before the last dose plus the lag time, will be flagged as TEAEs. The lag time is defined by the Pfizer Standard of 365 days post last dose. The algorithm will not consider any events that started prior to the first dose date. If an AE starts on the same day as the first dose date, it will be considered treatment emergent unless the CRF data indicates otherwise via explicitly recording time for AE onset which was occurred before the first treatment dosing.

Local toleration of skin irritation assessment will be assessed as specified in the Schedule of Activities (SoA) given in the protocol, by Draize scoring and via clinical observation (see Section 8.2.5 in the protocol).

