5.3.2. Caffeine, Alcohol, and Tobacco

- Participants will abstain from caffeine-containing products for 24 hours prior to the start of dosing and during confinement in the CRU.
- Participants will abstain from alcohol for 24 hours prior to admission to the CRU and continue abstaining from alcohol until collection of the final PK sample. Participants may undergo an alcohol breath test or blood alcohol test at the discretion of the investigator.
- Participants will abstain from the use of tobacco- or nicotine-containing products for 24 hours prior to dosing and during confinement in the CRU.

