8. STUDY ASSESSMENTS AND PROCEDURES

The investigator (or an appropriate delegate at the investigator site) must obtain a signed and dated ICD before performing any study-specific procedures.

Study procedures and their timing are summarized in the SoA. Protocol waivers or exemptions are not allowed.

Safety issues should be discussed with the sponsor immediately upon occurrence or awareness to determine whether the participant should continue or discontinue study intervention.

Participants will be screened within 28 days prior to application of the study intervention to confirm that they meet the study population criteria. If the time between screening and dosing exceeds 28 days as a result of unexpected delays (eg, delayed drug shipment), then participants do not require rescreening if the laboratory results obtained prior to first dose administration meet eligibility criteria.

A participant who qualified for this protocol but did not enroll from an earlier cohort/group may be used in a subsequent cohort/group without rescreening, provided laboratory results obtained prior to the first dose administration meet eligibility criteria for this study. In addition, other clinical assessments or specimen collections, eg, banked biospecimens, may be used without repeat collection, as appropriate.

Immediate safety concerns should be discussed with the sponsor immediately upon occurrence or awareness to determine if the participant should continue or discontinue study intervention.

Adherence to the study design requirements, including those specified in the SoA, is essential and required for study conduct.

All screening evaluations must be completed and reviewed to confirm that potential participants meet all eligibility criteria. The investigator will maintain a screening log to record details of all participants screened and to confirm eligibility or record reasons for screening failure, as applicable.

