8.3.1. Time Period and Frequency for Collecting AE and SAE Information

The time period for actively eliciting and collecting AEs and SAEs ("active collection period") for each participant begins from the time the participant provides informed consent, which is obtained before the participant's participation in the study (ie, before undergoing any study-related procedure and/or receiving study intervention), through and including a minimum of 28 calendar days after the last administration of the study intervention.

Follow-up by the investigator continues throughout and after the active collection period and until the AE or SAE or its sequelae resolve or stabilize at a level acceptable to the investigator.

For participants who are screen failures, the active collection period ends when screen failure status is determined.

If the participant withdraws from the study and also withdraws consent for the collection of future information, the active collection period ends when consent is withdrawn.

If a participant permanently discontinues or temporarily discontinues study intervention because of an AE or SAE, the AE or SAE must be recorded on the CRF and the SAE reported using the CT SAE Report Form.

Investigators are not obligated to actively seek information on AEs or SAEs after the participant has concluded study participation. However, if the investigator learns of any SAE, including a death, at any time after a participant has completed the study, and he/she considers the event to be reasonably related to the study intervention, the investigator must promptly report the SAE to Pfizer using the CT SAE Report Form.

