10.3.1. Definition of AE

AE Definition		
•	An AE is any untoward medical occurrence in a patient or clinical study participant, temporally associated with the use of study intervention, whether or not considered related to the study intervention.	
•	Note: An AE can therefore be any unfavorable and unintended sign (including an abnormal laboratory finding), symptom, or disease (new or exacerbated)	

Events Meeting the AE Definition

•	Any abnormal laboratory test results (hematology, clinical chemistry, or
	urinalysis) or other safety assessments (eg, ECG, radiological scans, vital sign
	measurements), including those that worsen from baseline, considered clinically
	significant in the medical and scientific judgment of the investigator. Any
	abnormal laboratory test results that meet any of the conditions below must be
	recorded as an AE:

- Is associated with accompanying symptoms;
- Requires additional diagnostic testing or medical/surgical intervention;
- Leads to a change in study dosing (outside of any protocol-specified dose adjustments) or discontinuation from the study, significant additional concomitant drug treatment, or other therapy.
- Exacerbation of a chronic or intermittent preexisting condition, including either an increase in frequency and/or intensity of the condition.
- New condition detected or diagnosed after study intervention administration, even though it may have been present before the start of the study.
- Signs, symptoms, or the clinical sequelae of a suspected drug-drug interaction.
- Signs, symptoms, or the clinical sequelae of a suspected overdose of either study intervention or a concomitant medication. Overdose per se will not be reported as an AE or SAE unless it is an intentional overdose taken with possible suicidal/self-harming intent. Such overdoses should be reported regardless of sequelae.

Events NOT Meeting the AE Definition

- Any clinically significant abnormal laboratory findings or other abnormal safety assessments that are associated with the underlying disease, unless judged by the investigator to be more severe than expected for the participant's condition.
- The disease/disorder being studied or expected progression, signs, or symptoms of the disease/disorder being studied, unless more severe than expected for the participant's condition.
- Medical or surgical procedure (eg, endoscopy, appendectomy): the condition that leads to the procedure is the AE.

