- Alternative causes, such as underlying disease(s), concomitant therapy, and other risk factors, as well as the temporal relationship of the event to study intervention administration, will be considered and investigated.
- The investigator will also consult the IB and/or product information, for marketed products, in his/her assessment.
- For each AE or SAE, the investigator must document in the medical notes that he/she has reviewed the AE or SAE and has provided an assessment of causality.
- There may be situations in which an SAE has occurred and the investigator has minimal information to include in the initial report to the sponsor. However, it is very important that the investigator always make an assessment of causality for every event before the initial transmission of the SAE data to the sponsor.
- The investigator may change his/her opinion of causality in light of follow-up information and send an SAE follow-up report with the updated causality assessment.
- The causality assessment is one of the criteria used when determining regulatory reporting requirements.
- If the investigator does not know whether or not the study intervention caused the event, then the event will be handled as "related to study intervention" for reporting purposes, as defined by the sponsor. In addition, if the investigator determines that an SAE is associated with study procedures, the investigator must record this causal relationship in the source documents and CRF, and report such an assessment in the dedicated section of the CT SAE Report Form and in accordance with the SAE reporting requirements.

Follow-Up of AEs and SAEs

- The investigator is obligated to perform or arrange for the conduct of supplemental measurements and/or evaluations, as medically indicated or as requested by the sponsor, to elucidate the nature and/or causality of the AE or SAE as fully as possible. This may include additional laboratory tests or investigations, histopathological examinations, or consultation with other healthcare providers.
- If a participant dies during participation in the study or during a recognized follow--up period, the investigator will provide Pfizer Safety with a copy of any postmortem findings, including histopathology.

- New or updated information will be recorded in the originally submitted documents.
- The investigator will submit any updated SAE data to the sponsor within 24 hours of receipt of the information.

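### The SAP's treatment-emergent rule goes by onset date alone, so an adverse event that opens before the first dose and worsens on treatment is counted or lost depending on how the site records it.

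*SAP*

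**What the plan says.** SAP 3.1.1 gives the rule: "An adverse event (AE) is considered a Treatment-Emergent Adverse Event (TEAE) if the event started during the effective duration of treatment". Two details follow. For onset before the first dose date, "The algorithm will not consider any events that started prior to the first dose date". For onset on the first dose date itself, "it will be considered treatment emergent unless the CRF data indicates otherwise", which requires an explicitly recorded onset time before dosing. Nothing in the section deals with an event that was already open and then worsens.

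SAP 6.1.1.1 leaves the AE tables to the sponsor's reporting standards and does not say whether they are restricted to treatment-emergent events.

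Three places in the protocol bear on this:

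- Section 8.3.1: active AE collection "begins from the time the participant provides informed consent".
- Section 10.3.1, among events that meet the AE definition: "Exacerbation of a chronic or intermittent preexisting condition, including either an increase in frequency and/or intensity of the condition".
- Section 10.3.3, under follow-up: "New or updated information will be recorded in the originally submitted documents".

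The primary endpoint in both documents covers how often systemic AEs occur and how severe they are, alongside laboratory tests, vital signs, ECG and application-site findings.

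**The concern.** The protocol treats a worsening as something that matters in its own right. The SAP's flag looks only at when an event began. An event that opens as mild on Day -1 and becomes moderate or severe under study drug is the kind of signal a first-in-human tolerability study is meant to show. With a single CRF record carrying a pre-dose start date, that event is excluded from the treatment-emergent tables, both as a case and as a severity grade.

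The exclusion comes from a stated rule, so a programmer following the SAP would apply it as written. Whether the event survives then turns on a recording choice that neither document specifies. In groups of four and two, one such choice visibly changes a primary summary.

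**Working it through.** The question is mainly one of definition, so the passages are set side by side first and the size is worked out after.

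**1. Can an AE be open at the first dose?** Yes. Collection starts at consent, and Protocol 8 says "Participants will be screened within 28 days prior to application of the study intervention", so there is a pre-dose window of up to about 28 days.

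**2. What does SAP 3.1.1 do in each case?**

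| Onset | How it is recorded | Flagged? |
|---|---|---|
| After the first dose | Own start date | Yes |
| Day 1 before dosing | No onset time | Yes |
| Day 1 before dosing | Onset time recorded | No |
| Before Day 1, worsens on treatment | New record dated at the worsening | Yes |
| Before Day 1, worsens on treatment | Original record updated | No |

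The last two rows describe the same clinical course with opposite results.

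**3. Do the documents settle which of those two rows applies?** No. Protocol 10.3.1 lets a worsened pre-existing condition stand as an AE, which favours a new record. Protocol 10.3.3 sends new information to the original documents, which favours the old one, but it does not mention start dates, severity changes or new AE lines. Protocol 10.1.7 refers CRF practice to a separate completion document that is not part of the material.

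**4. Group sizes.** Protocol 1.1 and 4.1 give approximately 6 per cohort, 4 active and 2 vehicle. Two planned cohorts give 2 × (4 + 2) = 12, matching the approximately 12 in Protocol 9.5. SAP 6.1.1 summarises vehicle by administration type (ointment or cream).

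**5. Effect of one missed participant on group incidence (100/n).**

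- Active, n = 4: 100/4 = 25 points.
- Vehicle, n = 2: 100/2 = 50 points.
- Vehicle with one optional cohort of the same type added, n = 4: 25 points. With two added, n = 6: 16.7 points.

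**6. Chance that a group contains at least one such participant.** The documents give no rate, so the per-participant probability p is an assumption. The formula is 1 − (1 − p)^n.

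| Assumed p | n = 4 | n = 2 |
|---|---|---|
| 1% | 3.9% | 2.0% |
| 5% | 18.5% | 9.8% |
| 10% | 34.4% | 19.0% |
| 20% | 59.0% | 36.0% |

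**7. Direction.** Within a group, a missed event can only lower the count. The contrast between groups has no fixed direction. As a hypothetical, let one of 4 active and one of 2 vehicle participants truly have an event: 25% − 50% = −25 points. If the active event is missed, the contrast is 0% − 50% = −50. If the vehicle event is missed, it is 25% − 0% = +25.

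**The case against.** The strongest reply is that nothing in the documents shows an event would actually be lost. Much of that reply stands.

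- A reader might infer that every pre-dose event that worsens is dropped. That goes too far: a worsening entered as a new AE with an on-treatment start is flagged, and a Day 1 event with no recorded time is counted.
- A reader might take Protocol 10.3.3 to mean that a worsening event must keep its pre-dose start date. The sentence sits among follow-up and reporting instructions and does not say so.
- A reader might infer that the whole primary endpoint is affected. The endpoint is worded in terms of AEs, and the SAP does not say its AE tables are limited to treatment-emergent events. Draize scores, laboratory data, vital signs and ECGs are summarised without the flag. The stopping rules in Protocol 6.5.1 and 6.5.2 do not refer to it either, so safety monitoring during the study is untouched.
- A reader might argue that pre-dose symptoms are to be expected because "Participants will abstain from caffeine-containing products for 24 hours prior to the start of dosing", with a similar rule for nicotine. The documents do not link abstinence to AEs. Eligibility also works against open events: participants are healthy and must have no acute disease within 7 days of Day 1.
- The 25 and 50 points follow from the group sizes. They would apply to any missed participant and do not measure how often this problem arises.

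What the reply does not remove is the rule itself. SAP 3.1.1 excludes earlier onsets without exception for worsening, and no text ensures that a worsening receives its own record.

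**Conclusion.** The concern holds in a limited form. An AE that starts between consent and first dose, and then increases in severity or becomes serious on treatment, is excluded from the treatment-emergent count and its severity when the site updates the original record. It is included when the site opens a new one. The plan leaves that choice open.

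The size is 25 points of incidence per missed participant in an active group of 4 and 50 points in a vehicle group of 2, smaller if optional cohorts enlarge the group. This rests on three conditions: such an event occurs, at a rate the documents do not give; the site does not open a new record; and the table in question uses the flag. The documents do not support a claim that the results will always look cleaner, because a miss in the vehicle group makes active treatment look worse by comparison.

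**What to change.** 1. In SAP 3.1.1, add that an AE with onset before the first dose is also treatment-emergent if it increases in severity or becomes serious on or after the first dose, and that it is tabulated at its worst post-dose severity.
2. Add one CRF completion instruction so that the date of worsening is captured, for example by closing the pre-dose record and opening a new one dated at the change. Protocol 10.3.3 asks for one intensity category per AE, so without this the pre-dose and post-dose severities may not be separable. A new record would already be flagged under the current rule; the SAP sentence covers cases where a site updates the old record instead.
3. In SAP 6.1.1.1, state whether the AE tables are limited to treatment-emergent events.

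The cost is two SAP sentences and one CRF line, with no new visit or assessment. The SAP's version history ties it to the original protocol, and its Cohort 4 assignment in Section 2.2 differs from the current Protocol 4.1, so these changes can go into an update that is needed anyway.
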